14.0.1 EXPANSION COHORT: BIOSTATISTICS

This study would be an expansion of our current study and therefore the data will ultimately be analyzed along with the data from our current study in which patients are receiving 2 cycles of BV. The goal of this expansion study is to determine whether the rate of FDG-PET normalization is improved with 3 cycles of BV when compared to 2 cycles. So far, we have observed a 28% rate of FDG-PET normalization following 2 cycles of BV; however an additional 14 patients (44%) were "good responders" to 2 cycles of BV and likely had the potential to achieve FDG-PET normalization had they received an additional cycle of BV. Based upon this, we estimate that the rate of FDG-PET normalization following 3 cycles of BV will be around 50%.

Allowing for type I and type II error rates of 0.2, and assuming a FDG-PET normalization rate of 28% with 2 cycles of BV, the number of patients required to show an improvement in FDG-PET normalization rate to 50% is 20.

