1.0 PROTOCOL SUMMARY AND/OR SCHEMA

In this study, we plan to treat patients with 2 cycles of weekly brentuximab vedotin (SGN-35); patients who achieve FDG-PET/CT normalization will proceed directly to autologous stem cell transplant (ASCT) and avoid salvage treatment with ifosfamide, carboplatin, and etoposide (ICE). Patients with persistent FDG-PET/CT abnormalities will receive 2 cycles of augmented ICE chemotherapy followed by repeat FDG-PET/CT. We aim to evaluate the rate of FDG-PET/CT normalization following 2 cycles of weekly brentuximab vedotin with or without augmented ICE in transplant eligible patients with relapsed or refractory HL. This study will enroll 46 patients.

Expansion Cohort

We will expand this study to include 20 additional patients. The expansion would again enroll patients who fail their front-line therapy for HL; however they will receive 3 cycles of weekly BV followed by reassessment by FDG-PET. Those who score Deauville 2 or better will proceed to ASCT while all others will receive 2 cycles of augmented ICE prior to consideration for ASCT. We aim to evaluate the rate of FDG-PET/CT normalization following 3 cycles of weekly brentuximab vedotin with or without augmented ICE in transplant eligible patients with relapsed or refractory HL.

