
Factors that predict response to ICE salvage therapy

All patients have received ICE-based ST for rel/ref HL at our institution since 1994; therefore we recently pooled this data to identify factors predictive of FI normalization following ICE. Between 9/1994 and 4/2010, 277 patients with rel/ref HL were treated on 1 of 4 studies described above. Two hundred and seventy-one patients underwent evaluation with FI before and after ST; 62% of these patients were evaluated with FDG-PET/CT. One hundred sixty-five (60%) patients achieved normalization of functional imaging following ST. Univariate and multivariate analysis to identify factors associated with failure to normalize FI was performed and four factors remained significant by multivariate analysis: bulk \geq 5cm, relapse within previously radiated fields, relapse within 1 year of initial treatment, and presence of B symptoms at relapse. The numbers of patients with 0, 1, 2, 3, or 4 risk factors were 31, 100, 83, 38, and 4 and the rate of FI normalization by risk factor group was 87%, 76%, 50%, 34%, and 0% respectively. Patients with 0-1 risk factors have a high rate of FI normalization with ICE ST and may be candidates for less intense therapy. In contrast, patients with 3-4 risk factors are at high risk for persistent FI abnormalities following ICE treatment and therefore may benefit from more novel salvage therapy, such as an antibody-

drug conjugate. As described below, brentuximab vedotin (SGN-35) is a highly effective treatment in rel/ref HL that is generally well tolerated and therefore may represent a better option for patients both at low risk and high risk of failing to normalize FI following ICE-based treatment, therefore we plan to treat all risk cohorts with brentuximab vedotin with or without augmented ICE and analyze the results according to risk group.

The majority of patients enrolled on the MSKCC studies described above had 0-2 risk factors (risk factors = b symptoms, extranodal disease, and relapse within 1 year). Since 2004, patients with all 3 risk factors were enrolled on a different study evaluating allogeneic stem cell transplant and therefore are not well represented in our ICE database. The true rate of FDG-PET/CT normalization following ICE chemotherapy is therefore likely lower than 60%. On this protocol, we will enroll patients with 0-3 risk factors and therefore we assumed a lower rate of FDG-PET/CT normalization from ICE chemotherapy in our biostatistics.

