As an additional criterion, we require that at least 7 out of the total 46 patients (15%) achieve FDG-PET/CT normalization after SGN-35 to call this new regimen a success. The purpose of this criterion is to exclude the situation that all patients may fail SGN-35 (i.e., persistent PET abnormalities) and hence must receive ICE salvage therapy, yet accidentally pass the above two-stage design. The threshold 15% was chosen because the previous phase I data show that about 30% of patients may achieve CR with SGN-35, and thus we believe it would be clinically meaningful to require at least 15% of patients to achieve PET normalization after SGN-35 to call it a success.

For the secondary objectives, we will report the stratified FDG-PET/CT normalization rates as sample proportions with their confidence intervals. Overall response rate to SGN-35 alone will be reported similarly. Toxicities will be summarized and tabulated. PFS and OS (see

definition in Section 12) will be analyzed using standard survival tools such as Kaplan-Meier estimation, log-rank tests and/or Cox regression models to incorporate various factors (such as Δ SUVmax, CD68, FoxP3, TIA-1, serum cytokine, etc.) and assess their correlation with PFS and/or OS. Competing risks analysis will be conducted if competing risk(s) exists (such as death without progression). Lab results including CD34 cell yield following mobilization will be reported as summary statistics.

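### The 3-cycle versus 2-cycle comparison runs across sequential, non-randomised cohorts with no risk adjustment, so its 0.2 error rates hold only if both cohorts carry the same underlying risk

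*Combined protocol and SAP*

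**What the plan says.** Section 14.0.1 gives the aim of the expansion as a comparison: "The goal of this expansion study is to determine whether the rate of FDG-PET normalization is improved with 3 cycles of BV" as against 2. It adds that "the data will ultimately be analyzed along with the data from our current study". The sample size is derived "assuming a FDG-PET normalization rate of 28% with 2 cycles of BV", a target of 50% with 3 cycles, and this allowance for error: "Allowing for type I and type II error rates of 0.2". The result is 20 patients. No test, sidedness, covariate or stratification is named.

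Section 1.0 also states a single-cohort aim, which needs no comparator: "We aim to evaluate the rate of FDG-PET/CT normalization following 3 cycles of weekly brentuximab vedotin".

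Section 3.0 shows that the expansion was proposed when 37 of the 46 patients had already accrued, so a patient's number of BV cycles is set by when they enrolled.

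For normalization by risk factor, section 14.0 says only "we will report the stratified FDG-PET/CT normalization rates as sample proportions with their confidence intervals". The regression models in that section are for PFS and OS.

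Section 3.0 also reports how strongly risk predicted normalization after ICE-based salvage. In the pooled data "four factors remained significant by multivariate analysis": bulk, relapse in an irradiated field, relapse within 1 year, and B symptoms. For 0 to 4 factors, "the rate of FI normalization by risk factor group was 87%, 76%, 50%, 34%, and 0% respectively".

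**The concern.** Without randomisation, the difference between cohorts combines the effect of the third cycle with any difference in who was enrolled. Baseline risk predicted normalization strongly after ICE-based salvage at this centre. If the same holds to some degree after BV, a shift in case mix between enrolment periods moves the normalization rate with no help from the third cycle.

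Chance imbalance is not the issue, because the nominal 0.2 already covers it. The issue is systematic drift, which no stated analysis would correct. A change in the patients could then be read as a benefit of the third cycle, or could hide one.

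**Working it through.** **Inputs.** 2-cycle rate 0.28, 3-cycle rate 0.50, error rates 0.2 and n = 20 (section 14.0.1). 2-cycle cohort 46 (section 1.0). Risk-factor counts 31/100/83/38/4 and ICE normalization rates 87/76/50/34/0% for 0 to 4 factors (section 3.0).

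**Step 1: reproduce n = 20.** For a one-sided pooled two-sample test of 46 against n,

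power = Φ{[(p₃ − p₂) − z₀.₈·SE₀] / SE₁}, with SE₀ = √[p̄(1 − p̄)(1/46 + 1/n)] and SE₁ = √[p₂(1 − p₂)/46 + p₃(1 − p₃)/n].

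At n = 20:
- p̄ = (46 × 0.28 + 20 × 0.50)/66 = 0.347
- SE₀ = 0.1275 and SE₁ = 0.1299
- (0.22 − 0.8416 × 0.1275)/0.1299 = 0.868, so power = 0.807

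At n = 19 power is 0.799, so 20 is the smallest size reaching 0.80. A two-sided 0.2 test at n = 20 gives 0.669. The stated figure therefore fits a one-sided unadjusted comparison with all 46 patients. That reading is inferred, since the section does not state it.

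**Step 2: error rates when underlying risk differs.** The same test, by exact binomial enumeration over all outcomes of 46 and 20, with the 2-cycle rate at 0.28:

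| True expansion rate | Meaning | P(declare improvement) |
|---|---|---|
| 0.28 | no effect, equal risk | 0.203 |
| 0.33 | no effect, case mix +5 points | 0.335 |
| 0.38 | no effect, case mix +10 points | 0.485 |
| 0.23 | no effect, case mix −5 points | 0.103 |
| 0.50 | planned effect, equal risk | 0.805 |
| 0.45 | planned effect, case mix −5 points | 0.687 |

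**Step 3: how much drift makes 5 points.** The gradient after BV alone is not given, so I assume that all, half or none of the ICE log-odds gradient carries over. The section 3.0 counts serve as the 2-cycle mix (mean 396/256 = 1.55 factors), and the 0% group is set to 5% so that it has a logit. With the full gradient, shifting the ICE logits by −1.66 gives BV rates of about 56/38/16/9/1% and 28% overall.
- Full gradient: +5 points needs a mix of about 20/45/26/8/1%, a mean of 1.25 factors.
- Half gradient: +5 points needs about 29/47/20/5/0%, a mean of 1.01.

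**Step 4: what adjustment does.** Simulation of 46 versus 20, one-sided 0.2, with 6,000 runs per cell (8,000 for no gradient). The cycle-3 effect is a constant odds ratio that gives 50% in the 2-cycle mix. The adjusted analysis is logistic regression on cohort plus risk-factor count.

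| Scenario | Quantity | Unadjusted | Adjusted |
|---|---|---|---|
| Full gradient, +5 points | false positives | 0.336 | 0.205 |
| Full gradient, −5 points (mean 1.87) | power | 0.642 | 0.822 |
| Full gradient, same mix | false positives | 0.207 | 0.211 |
| Full gradient, same mix | power | 0.803 | 0.841 |
| Half gradient, +5 points | false positives | 0.346 | 0.206 |
| Half gradient, same mix | power | 0.803 | 0.812 |
| No gradient, same mix | false positives | 0.207 | 0.208 |
| No gradient, same mix | power | 0.811 | 0.811 |

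The 0.642 is below the 0.687 of step 2 because a constant odds ratio in that higher-risk mix gives a 3-cycle rate of about 43%, not 45%.

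**Cross-check by another method.** A Mantel-Haenszel test stratified by 0–1 versus 2 or more factors (100,000 runs) was run with the expansion share having 0–1 factors going from 31% to 81%, against 51% in the 2-cycle cohort. It holds type I error at 0.20 and power at 0.81 to 0.84. The unadjusted test gives 0.09 to 0.44 and 0.62 to 0.95.

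**The case against.** **No drift is documented.** One set of eligibility criteria and one definition of normalization (Deauville 1–2) serve both cohorts, and the expansion follows directly on the first. With the half gradient, 5 points needs the mean count to fall from 1.55 to 1.01, more than half the between-patient standard deviation of 0.94. This stands as a limit on likelihood. But eligibility restricts none of the four factors, and section 3.0 itself says that sending patients with three risk factors to another study probably made the ICE normalization rate look too high.

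**Risk is partly covered.** Sections 2.0, 3.0 and 14.0 plan results by risk group, which could expose an imbalance. That is description. It does not adjust the comparison, and an adjustment chosen after seeing the imbalance is not prespecified.

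**The inputs are borrowed.** The gradient is for ICE-based salvage, with 62% of patients imaged by FDG-PET/CT, and section 3.0 suggests that this trial's mix is higher risk than the ICE database. Both points stand, so the simulated sizes are illustrative. The step 2 figures need neither input.

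**The test is inferred.** The text also fits a single-arm test against a fixed 28%. That does not escape the problem: with success at 8 or more of 20, type I error is 0.171 at 28%, 0.327 at 33% and 0.511 at 38%.

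**Equal risk is not sufficient.** The 28% is 9 of 32 patients already observed. Conditional on that result and with no drift, the same test has type I error 0.17, 0.26 or 0.36 if the true rate is 28%, 33% or 38%. This is correct, and risk adjustment does not cure it.

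**The adjustment omits extranodal disease**, which secondary objective 1 lists. The four factors proposed are those that section 3.0 reports as significant in the multivariate analysis of normalization.

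**Little depends on it.** The primary Simon test is untouched and no go/no-go rule is attached. That limits the severity, but the comparison is still the stated goal of the expansion.

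**Conclusion.** The concern holds. The sample size is not miscalculated, but its 0.2 error rates need an unstated condition, equal underlying risk in the two cohorts, and no planned analysis protects the comparison if that condition fails. A case-mix shift of 5 points raises the false-positive rate from 0.20 to 0.34, or lowers power from 0.80 to 0.69; a 10-point upward shift raises the false-positive rate to 0.48.

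These figures assume the inferred one-sided 46-versus-20 test and a true 2-cycle rate of 28%. The amount of drift, and the gradient after BV used to assess adjustment, are assumptions. The simulation lets only the adjusted factor differ, so it shows what adjustment for measured risk can do, not protection from other differences between cohorts. The change should be made; the primary analysis is unaffected.

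**What to change.** Keep n = 20 and add to section 14.0.1 wording such as:

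> Post-BV FDG-PET normalization (Deauville 1–2) in the 20 expansion patients will be compared with the final 46-patient 2-cycle cohort at one-sided 0.2, by logistic regression on cohort plus the count (0–4) of: bulk of 5 cm or more, relapse in a previously radiated field, relapse within 1 year, and B symptoms. The 28% is a planning value, not a fixed null.

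Report the risk-standardised difference with its confidence interval beside the crude difference, tabulate the risk factors by cohort, and label the comparison non-randomised and exploratory.

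**Cost.** Some SAP wording, one model and one table. No extra patients are needed, and secondary objective 1 already requires the four factors.

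**Limits.** The model rests on about 23 expected normalizations (46 × 0.28 + 20 × 0.50 = 22.9). The 95% interval for the crude difference stays wide, at about ±1.96 × √(0.28 × 0.72/46 + 0.50 × 0.50/20) = ±25 points. Unmeasured differences between enrolment periods remain.

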15.0 RESEARCH PARTICIPANT REGISTRATION AND RANDOMIZATION PROCEDURES

15.1 Research Participant Registration

Confirm eligibility as defined in the section entitled Criteria for Patient/Subject Eligibility.

Obtain informed consent, by following procedures defined in section entitled Informed Consent Procedures.

During the registration process registering individuals will be required to complete a protocol specific Eligibility Checklist.

All participants must be registered through the Protocol Participant Registration (PPR) Office at Memorial Sloan-Kettering Cancer Center. PPR is available Monday through Friday from 8:30am – 5:30pm at [contact]. Registrations must be submitted via the PPR Electronic Registration System (<http://ppr/>). The completed signature page of the written consent/RA or verbal script/RA, a completed Eligibility Checklist and other relevant documents must be uploaded via the PPR Electronic Registration System.

16.0 DATA MANAGEMENT ISSUES

A Research Study Assistant (RSA) will be assigned to the study. The responsibilities of the RSA include project compliance, data collection, abstraction and entry, data reporting, regulatory monitoring, problem resolution and prioritization, and coordination of the activities of the protocol study team.

The data collected for this study will be entered into the Clinical Research Database (CRDB). Source documentation will be available to support the computerized patient record.

Data to be collected will include:

1. Patient related features:

- age
- sex

2. Disease related features

- prior therapy
- disease status- relapsed vs. primary refractory
- results of all tests related to the study
- disease status at long-term follow-up

3. Treatment related

- duration of treatment
- stem cell yields
- response to treatment
- toxicities of treatment

16.1 Quality Assurance

Registration reports will be generated to monitor patient accruals and completeness of registration data. Routine data quality reports will be generated to assess missing data and inconsistencies. Accrual rates and extent and accuracy of evaluations and follow-up will be monitored periodically throughout the study period and potential problems will be brought to the attention of the study team for discussion and action

Random-sample data quality and protocol compliance audits will be conducted by the study team, at a minimum of two times per year, more frequently if indicated.

Retention of Records: All documentation of adverse events, records of study drug receipt and dispensation, and all IRB correspondence will be retained for at least 3 years after the investigation is completed.

16.2 Data and Safety Monitoring

The Data and Safety Monitoring (DSM) Plans at Memorial Sloan-Kettering Cancer Center were approved by the National Cancer Institute in September 2001. The plans address the new policies set forth by the NCI in the document entitled "Policy of the National Cancer Institute for Data and Safety Monitoring of Clinical Trials" which can be found at <http://www.cancer.gov/clinicaltrials/conducting/dsm-guidelines>. The DSM Plans at MSKCC were established and are monitored by the Office of Clinical Research. The MSKCC Data

and Safety Monitoring Plans can be found on the MSKCC Intranet at:

<http://mskweb5.mskcc.org/intranet/html/99073.cfm>

There are several different mechanisms by which clinical trials are monitored for data, safety and quality. There are institutional processes in place for quality assurance (e.g., protocol monitoring, compliance and data verification audits, therapeutic response, and staff education on clinical research QA) and departmental procedures for quality control, plus there are two institutional committees that are responsible for monitoring the activities of our clinical trials programs. The committees: Data and Safety Monitoring Committee (DSMC) for Phase I and II clinical trials, and the Data and Safety Monitoring Board (DSMB) for Phase III clinical trials, report to the Center's Research Council and Institutional Review Board.

During the protocol development and review process, each protocol will be assessed for its level of risk and degree of monitoring required. Every type of protocol (e.g., NIH sponsored, in-house sponsored, industrial sponsored, NCI cooperative group, etc.) Will be addressed and the monitoring procedures will be established at the time of protocol activation.

Section 16.3 Regulatory Documentation

Prior to implementing this protocol at MSK, the protocol, informed consent form, HIPAA authorization and any other information pertaining to participants must be approved by the MSK Institutional Review Board/Privacy Board (IRB/PB). There will be one protocol document and each participating site will utilize that document.

Participating sites that are conducting data analysis should submit this protocol to their IRB according to local guidelines. Copies of any site IRB correspondence should be forwarded to MSK.

17.0 PROTECTION OF HUMAN SUBJECTS

Potential Risks

Traditionally, we have used ICE chemotherapy as the initial salvage therapy in relapsed/refractory HL. In this study, ICE chemotherapy is either eliminated or delayed until treatment with SGN-35 is completed. In the phase II studies described above, SGN-35 was associated with tumor reduction in over 90% of patients with relapsed/refractory HL. While delaying or eliminating ICE chemotherapy represents a potential risk for patients enrolled in this protocol, this potential risk is minimal given the high activity of SGN-35.

Potential Benefits

While ICE-based salvage treatment is commonly administered for relapsed/refractory HL it is associated with significant toxicity. Patients enrolled on this trial who achieve FDG-PET/CT negativity following 2 cycles of SGN-35 will proceed directly to ASCT. Therefore, a portion of patients enrolled on this study may avoid ICE-based treatment. Furthermore, Seattle Genetics is supplying SGN-35 free of charge.

Provisions for preventing and treating adverse events

Assessment for neuropathy will be performed before each cycle of brentuximab vedotin. Treatment of febrile neutropenia, cytopenias, ifosfamide-related gross and microscopic

hematuria, and catheter related sepsis, thrombosis, and pneumothorax will be in accordance with standard medical practices employed at MSKCC.

Patients will receive standard anti-emetics as prophylaxis against nausea and vomiting.

Alternatives/Options for treatment

For patients eligible, alternative therapy would consist of ICE-based salvage therapy or DHAP chemotherapy.

Costs

The patient will be responsible for all costs related to treatment and complications of treatment, including G-CSF, pegfilgrastim, FDG-PET scans, and all hospitalizations.

SGN-35 will be supplied by Seattle Genetics free of charge. The patient will not be responsible for the cost of correlative studies.

Participation in this study is voluntary and patients will not be paid for participation.

Privacy and confidentiality

Confidentiality will be maintained within the limits of the law. Only qualified individuals from MSKCC; the National Cancer Institute; the FDA; Seattle Genetics; will be able to review patients' medical records. Neither the patients' names nor other identifying information will be used in reports or publications arising from this study. After all patients have completed treatment on study and primary data analysis is complete, FDG-PET/CT scans will be de-identified (only patient weight and study ID number will be shared) and sent on a CD via mail to LYSA Imaging at Hôpitaux Universitaires Henri Mondor, France for data analysis.

17.1 Privacy

MSKCC's Privacy Office may allow the use and disclosure of protected health information pursuant to a completed and signed Research Authorization form. The use and disclosure of protected health information will be limited to the individuals described in the Research Authorization form. A Research Authorization form must be completed by the Principal Investigator and approved by the IRB and Privacy Board (IRB/PB).

